7.3.5.1 Corrected QT Intervals

The terminology QTc is used in this section as a general notation for QTc using any of the specified methods.

The QT interval data will be corrected for heart rate using 2 correction methods (QTcF and corrected QT interval by Bazett – QTcB). For each QTc correction method, the relationship between QTc and RR at baseline will be evaluated graphically by plotting the logarithm of baseline QTc values against the logarithm of corresponding RR intervals. QTcF will be used as the primary correction method for statistical analysis. If the correlation between QTc and RR intervals remains significant using the Fridericia correction method, an alternative correction method may be considered for statistical analysis in addition to QTcF.

For the statistical analysis based on the primary correction method (QTcF), the mean changes from baseline (Δ QTc) at each time point will be summarized (mean, standard deviation, median and

range, and 2-sided 90% CI). Mean values for the difference and 2 sided 90% CI for mean difference will be calculated at each time point.

The primary analysis will focus on the maximum mean change from baseline in QTc (Δ QTc) on Cycle 1 Day 15, which will be estimated by the mean QTc change at around t_{max} , the time when the C_{max} is reached (i.e., steady state). The same analysis will be performed for Δ QT data using other correction methods if data warrant. The mean change from baseline in QTc (\pm standard deviation) over time will be plotted.

In addition, QTc will be categorized based on International Council for Harmonisation (ICH) E14 guidelines. Tables will present the number and percentage of patients meeting or exceeding the following categories:

- QTc prolongation:
 - Absolute values >450 to ≤ 480 msec
 - Absolute values >480 to ≤ 500 msec
 - Absolute values >500 msec
- QTc change from baseline:
 - Increase from baseline >30 to ≤ 60 msec
 - Increase from baseline >60 msec

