3 OBJECTIVES AND ENDPOINTS

Table 1 Objectives and Corresponding Endpoints

Tier	Objectives	Endpoints
Primary – Dose Escalation	To determine MTD and/or RP2D of HMPL-689 in patients with relapsed, refractory, or resistant lymphoma	
 • Incidence of DLTs • Safety (including but not limited to TEAEs, treatment-related adverse events [TRAEs], SAEs, treatment-related SAEs [TRSAEs], and lab abnormalities)
Primary – Dose Expansion	To further evaluate safety and tolerability of HMPL-689 at MTD in patients with relapsed, refractory, or resistant lymphoma	
 • Safety, including TEAEs and TRAEs
Secondary	To assess preliminary efficacy of HMPL689 in patients with relapsed, refractory, or resistant lymphoma overall and by lymphoma sub-types as assessed by investigator	
 • ORR • TTR • DoR • CBR • PFS
	To characterize PK parameters of HMPL-689 in patients with relapsed, refractory, or resistant lymphoma at both dose escalation and dose expansion stages	
 • Concentration-time profiles and PK parameters after single dose and at steady state
	To evaluate the effect of HMPL-689 on cardiac repolarization, as detected by changes in electrocardiogram (ECG) QTc intervals	
 • QTc interval and HMPL-689 concentration

Abbreviations: CBR = clinical benefit rate; DLT = dose-limiting toxicity; DoR = duration of response; MTD = maximum tolerated dose; ORR = objective response rate; PD = progressive disease; PFS = progression-free survival; PK = pharmacokinetic; RP2D = recommended phase 2 dose; SAE = serious adverse event; TEAE = treatment-emergent adverse event; TRAE = treatment-related adverse event; TRSAE = treatment-related serious adverse event; TTR = time to response.

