4.1.1 Dose Escalation Stage (Stage 1)

Dose escalation will be performed according to an mTPI-2 ([Yang 2015](#)). HMPL-689 dose escalation will be titrated using a modified Fibonacci design allowing dose increments in subsequent dose levels as listed in [Table 2](#). The guidelines used for dose escalation are shown in [Figure 1](#).

Table 2 Proposed Dose Escalation Scheme

Cohort	Dose Level ^a	Route of Administration
-1	2.5 mg QD	Orally, with water
1	5 mg QD	Orally, with water
2	10 mg QD	Orally, with water
3	15 mg QD	Orally, with water
4	20 mg QD	Orally, with water
5	25 mg QD	Orally, with water
6	30 mg QD	Orally, with water
7	35 mg QD	Orally, with water
8	40 mg QD	Orally, with water
9	45 mg QD	Orally, with water
10	50 mg QD	Orally, with water
X ^b	XX ^b	Orally, with water

Abbreviations: PK = pharmacokinetic; QD = once daily; SRC = safety review committee.

^a The actual next dose will be discussed and decided by the investigators and sponsors based on all previous available data.

^b The need for dose escalation beyond 50 mg QD, or other regimens, such as twice daily, will be evaluated and determined by the SRC based on all available cumulative clinical safety, PK, and efficacy data.

Figure 1 mTPI-2 Decision Chart for Selection of Dose

Number of Patients in a Cohort

	1	2	3	4	5	6	7	8	9	10	11	12
0	E	E	E	E	E	E	E	E	E	E	E	E
1	D	D	S	S	E	E	E	E	E	E	E	E
2		D	D	D	D	S	S	S	E	E	E	E
3			DU	DU	D	D	D	D	S	S	S	S
4				DU	DU	DU	D	D	D	D	D	S
5					DU	DU	DU	DU	DU	D	D	D
6						DU	DU	DU	DU	DU	DU	D
7							DU	DU	DU	DU	DU	DU
8								DU	DU	DU	DU	DU
9									DU	DU	DU	DU
10										DU	DU	DU
11											DU	DU
12												DU

DLT = dose limiting toxicity, E = escalate to the next higher dose; S: Stay at the same dose, D = de-escalate to the previous lower dose, DU = de-escalate to the previous lower dose and the current dose will never be used again in the trial.

Target toxicity probability = 30%; epsilon 1 = 0.05; epsilon 2 = 0.05.

The design characteristics of mTPI-2 are as follows:

- The maximum sample size for this stage will be determined by the sponsor and investigators, based on the accumulated data and the mTPI-2 method (Ji 2013). The maximum recommended sample size under mTPI-2 design is $k \times (d + 1)$, where k denotes the cohort size and d denotes the number of doses. In this study, the minimum cohort size is 3.
- The equivalence interval of toxicity probability for MTD is (25%, 35%). This interval is derived based on the following parameters:

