5.7.11 Electrocardiogram

All electrocardiograms (ECGs) are required to be performed using a 12-lead tracing. ECG measurements will include PR interval, QRS interval, RR interval, QT/QTcF interval, and heart rate.

For dose escalation stage, triplicate ECGs, approximately 2 minutes apart, should be performed at screening, pre-dose, and 2 ± 0.5 and 4 ± 0.5 hours post-dose on Days 1 and 15 of Cycle 1 in order to evaluate concentration-QT relationship with HMPL-689. Single ECG will be conducted at any time on Day 1 of every cycle from Cycle 2 and onwards, and at study completion or early termination. For dose expansion stage, ECGs should be collected according to the schedule and time points in [Appendix 3](#).

Additional ECGs and other cardiac monitoring will be provided as clinically indicated during the study.

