17.5. ECG EVALUATIONS

Results from the central ECG (Electrocardiogram) Reading Centre will be included in the reporting of this study.

The following ECG parameters will be reported:

Protocol Number: 2018-689-00US1 Page 41 of 43

- PR Interval (msec)
- RR Interval (msec)
- QRS Interval (msec)
- QT Interval (msec)
- QTcF Interval (msec) = QT interval/cube root of RR interval $\frac{QT \ (ms)}{\sqrt[3]{RR \ (ms)/1000}}$
- HR (bpm)
- Overall assessment of ECG (Investigator's judgment):
 - Normal
 - Abnormal, Not Clinically Significant
 - Abnormal, Clinically Significant

All ECG evaluation data will be listed

-

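### The QTc endpoint pairs QTc with drug concentration, but neither the protocol nor the SAP specifies or points to an analysis that relates the two

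*Protocol*

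**What the plan says.** Protocol section 3, Table 1, lists as a secondary endpoint "QTc interval and HMPL-689 concentration", under the objective on cardiac repolarization. SAP Table 1 repeats it. Amendment 5 left this objective in place.

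Protocol 5.7.11 schedules Stage 1 triplicate ECGs at screening and, on Days 1 and 15 of Cycle 1, before dosing and at 2 and 4 hours after it, "in order to evaluate concentration-QT relationship with HMPL-689". Stage 2 ECG times are in Appendix 3.

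The analysis is in Protocol 7.3.5.1. Changes in QTcF at each time point "will be summarized (mean, standard deviation, median and" "range, and 2-sided 90% CI". Then: "The primary analysis will focus on the maximum mean change from baseline in QTc" on Cycle 1 Day 15, "which will be estimated by the mean QTc change at around" tmax. Tables of QTc categories follow. Protocol 7.3.3 describes PK summaries and leaves details to a PK analysis plan. The synopsis adds population modelling of plasma concentration, but not of QTc.

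SAP 17.5 names the ECG parameters to be reported and ends: "All ECG evaluation data will be listed". SAP section 2 leaves PK to a separate plan.

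**The concern.** The endpoint and the stated reason for taking the ECGs both call for an estimate of how QTc changes with concentration. The only analyses written down use time after dose and ignore the measured concentration. If the plan is followed literally, the study reports a mean change and some category counts, and the relationship it set out to examine is left unestimated.

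At Stage 1 dose levels the by-time-point mean is also imprecise: "In this study, the minimum cohort size is 3". It has a loose anchor as well. Protocol 7.3.5.1 does not tie the period around tmax to a fixed ECG time, and Protocol 5.2.4 allows dosing with or without food. In the food-effect study (Protocol 2.3) median tmax was 1.0 hour fasted and 4.0 hours fed. A model driven by measured concentration does not need every patient to peak at the same clock time.

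**Working it through.** The documents give no SD, precision target or sample size for QTc, so there is no planned figure to reproduce. The check has two parts.

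**1. Is a concentration-QTc analysis specified anywhere?**

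| Place | Content on QTc and concentration |
|---|---|
| Protocol Table 1, SAP Table 1 | Endpoint names both |
| Protocol 5.7.11 | Stage 1 ECGs taken to study the relationship |
| Protocol 7.3.3 and synopsis | PK summaries and population PK; no QTc model |
| Protocol 7.3.5.1 | Mean change by time point, 90% CI, category tables; no concentration term |
| SAP 17.5 | Parameters reported and listed; no change summary, CI, category table or model |

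None is specified, and there is no cross-reference to one.

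**2. What does this cost in precision?**

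Inputs from the documents: two-sided 90% CI (7.3.5.1); minimum Stage 1 cohort of 3 (4.1.1); 10 planned dose levels (Table 2); about 100 patients expected in Stage 2 (Amendment 5 summary; the body text is redacted). Assumed, because the documents are silent: SD of change 8 to 15 msec.

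By-time-point half-width = t(0.95, n-1) x SD / sqrt(n). For n = 3: 2.920 / 1.732 = 1.69, so 1.69 x 8 = 13.5 msec and 1.69 x 15 = 25.3 msec.

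| n | Multiple of SD | SD 8 | SD 10 | SD 15 |
|---|---|---|---|---|
| 3 | 1.69 | 13.5 | 16.9 | 25.3 |
| 6 | 0.82 | 6.6 | 8.2 | 12.3 |
| 20 | 0.39 | 3.1 | 3.9 | 5.8 |
| 50 | 0.24 | 1.9 | 2.4 | 3.6 |
| 100 | 0.17 | 1.3 | 1.7 | 2.5 |

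Comparator: a linear model of change in QTcF on concentration with a random patient intercept. The result is the 90% half-width of the predicted change at the Day 15 peak for 30 mg, used here only as an example dose. Further assumptions are exposure proportional to dose, 40% between-patient CV in exposure, 30 to 70% of the QTc variance lying between patients, and 5 ECG/PK pairs per patient. The 5 pairs follow from 5.7.11: 2 and 4 hours on Day 1, then predose, 2 and 4 hours on Day 15, with Day 1 predose as baseline. The half-width is t(0.95, patients - 2) times the generalized least squares standard error.

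| Stage 1 data pooled | Half-width, SD 8 to 15 | n = 3 interval is wider by |
|---|---|---|
| 10 levels x 3 = 30 patients | 1.8 to 4.2 msec | 6.0 to 7.4 times |
| 6 levels x 3 = 18 patients | 3.6 to 7.0 msec | 3.6 to 3.7 times |

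Part of each ratio comes from the t quantile on 2 degrees of freedom. In standard errors alone the ratios are 3.5 to 4.3 and about 2.2.

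Stage 2, all at one dose, SD 10:

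| n | By-time-point | Model | Ratio |
|---|---|---|---|
| 20 | 3.87 | 2.85 to 3.48 | 1.1 to 1.4 |
| 50 | 2.37 | 1.72 to 2.12 | 1.1 to 1.4 |
| 100 | 1.66 | 1.20 to 1.49 | 1.1 to 1.4 |

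**The case against.** A reader might infer that the repolarization objective cannot be answered with useful precision. The documents do not support that. Protocol 7.3.5 is not confined to Stage 1, Stage 2 also collects ECGs, and SAP section 8 gives non-efficacy results for each stage in total as well as by group. About 100 patients at one dose would give a half-width of 1.3 to 2.5 msec if all were pooled and evaluable. The exclusions in 7.3.5 will lower that number, but at SD 10 even 50 patients give 2.4 msec, as good as the pooled Stage 1 model. This part of the objection stands, and it confines the precision argument to Stage 1 dose levels.

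The Stage 1 comparison is also unequal: 3 patients at one time point against 18 or 30 patients with 5 pairs each. Much of the gain is pooling, which requires the linear model to be right. That stands too.

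It is tempting to join the extremes of the food-effect study, 0.5 to 8 hours, and conclude that ECGs at 2 and 4 hours miss the peak. That leaves out the first-in-human study in Protocol 2.3, where fed medians were 1.5 to 3 hours. The anchor is loose, but it is not shown to fail.

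Finally, the PK analysis plan may already contain the model. It was not available here, so its absence there cannot be claimed. What can be said is that neither the protocol nor the SAP refers to such a model.

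**Conclusion.** The mismatch stands on the documents alone and needs no assumed figure: the endpoint and the purpose of the Stage 1 ECGs require an analysis of QTc against concentration, and neither document specifies or cites one. SAP 17.5 widens the gap by leaving out the change-from-baseline and category summaries that Protocol 7.3.5.1 does specify.

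The precision loss is real but local. It applies to Stage 1 dose levels of about 3 and is small in Stage 2. All msec figures rest on the assumed SD. The model figures also rest on linearity, matched samples and the number of dose levels actually run.

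A reader might go further and conclude that the primary analysis in 7.3.5.1 has to be replaced. That does not follow. It ranks analyses within one secondary objective of a phase 1 study, no test or decision threshold is attached to it, and nothing in the section prevents a model being added beside it.

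**What to change.** In Protocol 7.3.5.1 and SAP 17.5, or by explicit reference to the PK analysis plan, pre-specify a linear mixed-effects model of change in QTcF on time-matched HMPL-689 concentration. Pool over doses and, where matched samples exist, over both stages. State the linearity check, and report the predicted change with its 90% CI at the geometric mean Cmax of the RP2D.

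Keep the by-time-point means and category tables and carry them into SAP 17.5. At the same time align the ECG baseline: Protocol 7.3.5 uses the mean of the predose triplicate on Cycle 1 Day 1, whereas SAP 7.2 uses the last assessment marked as predose.

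The cost is some wording and one extra model, with no planned new data collection. The model depends on linearity and on PK samples matched to the ECGs. The stated purpose in Protocol 5.7.11 suggests matching, but the sampling tables in Appendices 2 and 3 were not available to confirm it. The study is open-label, so the addition should be made and dated before database lock.

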7.3.5.2 Heart Rate, QRS, and PR Intervals

For each treatment and time point of measurement, heart rate, QRS interval, and PR interval, as well as the change from baseline in heart rate, QRS, and PR (Δ heart rate, Δ QRS, Δ PR), will be summarized using descriptive statistics (mean, standard deviation, median, range, and 90% CI). The number and percentage of patients with heart rate >100 bpm will be tabulated for each time point. The number and percentage of patients with QRS >110 msec will be tabulated for each time point. The number and percentage of patients with PR >200 msec will be tabulated for each time point.

7.4 Interim Analysis

There is no interim analysis planned for this study.

8 ETHICS

8.1 Institutional Review Board/Independent Ethics Committee (IRB/IEC)

This protocol, the Informed Consent Forms, any information to be given to the patient and relevant supporting information must be submitted to the IRB/IEC by the Principal Investigator for review and approval before the study is initiated. In addition, any patient recruitment materials must be approved by the IRB/IEC.

The Principal Investigator is responsible for providing written summaries of the status of the study to the IRB/IEC annually or more frequently in accordance with the regulatory requirements and policies and procedures established by the IRB/IEC. Investigators are also responsible for promptly informing the IRB/IEC of any protocol changes or amendments and of any unanticipated problems involving risk to human patients or others.

In addition to the requirements to report protocol-defined AEs to the sponsor or sponsor's designee, investigators are required to report to their respective IRB/IEC promptly all unanticipated problems involving risk to human patients. Some IRBs/IECs may want prompt notification of all SAEs, whereas others require notification only about events that are serious, assessed to be related to study treatment, and are unexpected.

8.2 Ethical Conduct of the Study

The study will be conducted in accordance with the protocol, International Conference on Harmonization (ICH) guidelines, applicable regulations and guidelines governing clinical study conduct and the ethical principles that have their origin in the Declaration of Helsinki.

8.3 Patient Information and Consent

The investigator or his/her representative, qualified by education, training, and experience to comply with GCP and applicable regulatory requirements, will provide verbal and written information to the patient explaining the nature of the study, and answering all questions. Prior to any study-related screening procedures being performed on the patient, the informed consent statement will be reviewed, signed, and dated by the patient and the person who administered the informed consent. The ICF must include a statement that the sponsor or its designee and regulatory authorities have direct access to subject records. A copy of the informed consent form will be given to the patient and the original will be placed in the patient's medical record and must be available for verification by study monitors at any time. If applicable, it will be provided in a certified translation of the local language.

The Informed Consent Form should be revised whenever there are changes to procedures outlined in the informed consent or when new information becomes available that may affect the willingness of the patient to participate.

For any updated or revised Consent Forms, the case history for each patient shall document the informed consent process and that written informed consent was obtained for the updated/revised Consent Form for continued participation in the study. Signed and dated Informed Consent Forms must remain in each patient's study file and must be available for verification by study monitors at any time.

8.4 Data Privacy and Confidentiality

The investigator and the sponsor or its designee must observe and adhere to any country data privacy laws and regulations (including country specific Data Protection Acts). The investigator and the sponsor or its designee are responsible for ensuring that sensitive information, transfer of data/research samples, and storage of biological material retained for future research is handled in accordance with local requirements. Appropriate consent for participation and understanding of the use and disclosure and/or transfer (if applicable) of protected information and research samples must be obtained.

Subject names will not be supplied to the sponsor or its designee. The sponsor maintains confidentiality standards by coding each patient enrolled in the study through assignment of a unique patient identification number. This means that patient names are not included in data sets that are transmitted to any sponsor location. Only the subject number and subject's initials (subject's initials will only be recorded if allowable by local regulations) will be recorded in the CRF, where permitted; if the patient's name appears on any other document (eg, laboratory report), it must be de-identified before submitting to the sponsor or its designee.

Patient medical information obtained by this study is confidential and may only be disclosed to third parties as permitted by the Informed Consent Form (or separate authorization for use and disclosure of personal health information) signed by the patient, unless permitted or required by law.

Medical information may be given to a patient's personal physician or other appropriate medical personnel responsible for the patient's welfare, for treatment purposes.

Study findings stored on a computer will be stored in accordance with local data protection laws. The subjects will be informed that data generated by this study must be available for inspection upon request by representatives of the China FDA and other national and local health authorities, study monitors, representatives, and collaborators, and the IRB/IEC for each study site, as appropriate and that all personal information made available for inspection will be handled in strictest confidence and in accordance with local data protection laws.

9 STUDY DOCUMENTATION, CASE REPORT FORM, AND RECORDS

9.1 Source Data Documentation

Study monitors will perform ongoing SDV to confirm that critical protocol data (i.e., source data) entered into the CRFs by authorized site personnel are accurate, complete, and verifiable from source documents.

Source documents are where patient data are recorded and documented for the first time. These include, but are not limited to, hospital records, clinical and office charts, laboratory notes, memoranda, patient diaries or evaluation checklists, pharmacy dispensing records, recorded data from automated instruments, copies of transcriptions that are certified after verification as being accurate and complete, microfiche, photographic negatives, microfilm or magnetic media, Xrays, patient files, and records kept at the pharmacy, laboratories, and medico-technical departments involved in a clinical trial.

Source documents that are required to verify the validity and completeness of data entered into the CRFs must never be obliterated or destroyed.

To facilitate SDV, the investigator(s) and institution(s) must provide the sponsor direct access to applicable source documents and reports for trial-related monitoring, sponsor audits, and IRB/IEC review. The investigational site must also allow inspection by applicable regulatory authorities.

9.2 Use of Computerized System

When clinical observations are entered directly into an investigational site's computerized medical record system (i.e., in lieu of original hardcopy records), the electronic record can serve as the source document if the system has been validated in accordance with FDA requirements pertaining to computerized systems used in clinical research. An acceptable computerized data collection system (for clinical research purposes) would be one that (1) allows data entry only by authorized individuals; (2) prevents the deletion or alteration of previously entered data and provides an audit trail for such data changes (e.g., modification of file); (3) protects the database from tampering; and (4) ensures data preservation.

If a site's computerized medical record system is not adequately validated for the purposes of clinical research (as opposed to general clinical practice), applicable hardcopy source documents must be maintained to ensure that critical protocol data entered into the CRFs can be verified.

